6.6.1 Participant Assessments

6.6.1.1 Screening and Baseline

Upon receipt of clinician- and self-referrals (further details on the recruitment methods are provided in section 6.8.1 Recruitment), the Research Associate based at UEA will describe the study to potential participants and send the Participant Information Sheet (PIS) via email. The PIS can also be sent via post if preferred. If the post option is selected, a screening and baseline pack consisting of an information sheet, consent form, eligibility checklist, baseline questionnaires and a prepaid return envelope will be sent so that participants have access to a paper version of all documents required at the subsequent session.

Participants who opt to take part in the study will be asked to provide fully informed written consent in the presence of the Research Associate based at UEA. The Research Associate will be present via video call or phone call. If an online consent form is selected, a simple typewritten electronic signature will be used following the HRA guidance on eConsent. Participants will also be asked to provide multiple forms of contact including email, mobile, landline and postal address.

Once online written consent has been obtained, participants will be asked to complete the online screening assessment hosted by the central database (REDCap), stored on servers based at NCTU. The screening assessment includes an eligibility checklist (a series of statements asking that they meet the eligibility criteria), demographic questions and the measure of anxiety (GAD7[30]). Participants meeting eligibility criteria and scoring five or above on the GAD7 will be asked to continue completing all baseline measures. Participants will also be asked to indicate their preferred method for follow-up assessments (online or via post). To minimise missing data, participants will be unable to submit any online questionnaire with any missing fields. This will be clearly explained in the PIS. Participants can select to use the paper version via post if preferred.

If the post option is selected, participants will be asked to return the signed consent form and the completed eligibility checklist, the GAD7, socio-demographic questions and baseline measures using a prepaid envelope. The Research Associate based at UEA will manually enter the data into the central database upon the receipt of documents.

6.6.1.2 Intervention

The eligibility criteria will be fully checked within a week from the completion of baseline assessments, and eligible participants will be randomised to iACT4CARERS plus TAU or TAU alone by NCTU. Participants randomised to iACT4CARERS plus TAU will receive a link to the iACT4CARERS website and login details from the unblinded Trial Manager based at NCTU via email (and post if requested). Unauthorised access to the intervention will be prevented by providing participants with unique login details. The allocated trial therapist will also receive a notification from the unblinded Trial Manager based at NCTU via email.

6.6.1.2 12-week and 24-week Follow-Ups

Twelve and twenty-four weeks after randomisation, participants will receive an email to ask them to complete the follow-up measure online from NCTU, if they have requested this. The email will include a reminder, which reiterates the reasons why this follow-up data is important. If the follow-up measure is not completed within a week, the Research Associate based at UEA who is blind to treatment allocation will be informed by NCTU and will give a follow-up phone call to check if the participant needs additional support for completing the online assessments. If the participant

decides not to complete the assessments, the Research Associate will ask them to provide a reason if possible. Participants, who have indicated that they wish to receive the follow-up measure via post, will receive the follow-up assessments via post from NCTU and will be asked to return them to NCTU using a prepaid envelope. The unblinded Trial Manager based at NCTU will give a follow-up phone call a week after the assessments have been posted to ensure that participants have received the follow-up measure and check if additional support is needed for completion. The unblinded Trial Manager based at NCTU will manually enter the data into the central database upon the receipt of documents. Participants will be asked not to reveal their allocation to the blinded Research Associate during follow-up calls.

Selected participants from the intervention arm will be invited to an individual interview at a 12week follow-up as part of the process evaluation. The interview is optional, and participants will receive a separate PIS and consent form for this part of the study if invited. Interviews will be conducted by the unblinded delegate based at NCTU via video call or telephone. Trial therapists and referrers will also be invited to interviews (see 6.5.3 Qualitative Study/Process Evaluation). If the interview is conducted by video call, the sound recording of the interview through the video conference software will be used to audio record the session. If the interview is conducted by telephone, a digital voice recorder will be used. An audio file of interview will be uploaded to a secure server at UEA immediately after the interview, and the original recording will be completely deleted from the software or voice recorder. The recording will be transcribed as soon as possible using software approved by UEA (e.g. EDCaption) or the external transcribing company. The audio files uploaded to the secure server at UEA will be deleted as soon as the accuracy of the transcripts has been confirmed.

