6.5 Outcomes

6.5.1 Primary Outcomes

The primary outcome is anxiety symptoms as assessed by the Generalized Anxiety Disorder-7 (GAD7[30]) at 12 weeks. Anxiety is equally or more prevalent than depression in family carers of people with dementia but is somewhat neglected in the current literature[3, 4]. A recent comprehensive meta-review of systematic reviews on nonpharmacological interventions (e.g. CBT, counselling) for dementia carers also demonstrated that the existing interventions are not effective for treating carer anxiety, while the efficacy of such interventions on carer depression is promising[32]. Our feasibility study demonstrated that iACT4CARERS is more beneficial in treating anxiety symptoms than depressive symptoms, suggesting that iACT4CARERS may have potential to overcome challenges observed in previous studies. Therefore, we will target anxiety symptoms as a primary outcome measure to fill the gap in the current literature.

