6.6.2 Early Stopping of Follow-up

If a participant chooses to discontinue their trial treatment, they should continue to be followed up as closely as possible to the follow-up schedule defined in the protocol, providing they are willing. They should be encouraged and facilitated not to leave the whole trial, even though they no longer take the trial treatment. If, however, the participant exercises the view that they no longer wish to be followed up, this view must be respected, and the participant withdrawn entirely from the trial. NCTU should be informed of the withdrawal in writing using the appropriate iACT4CARERS trial documentation. Data already collected will be kept and included in analyses according to the intention-to-treat principle for all participants who stop follow-up early.

Participants who stop trial follow-up early will not be replaced.

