6.8.2 Retention

We will minimise loss to follow-up in a number of ways. Our feasibility study demonstrated that the content of iACT4CARERS was acceptable and positively received by family carers[44], although 27% of carers were lost to follow-up[22]. Thus, we have inflated our sample size estimate to allow for a dropout rate of 30%. We will include detailed explanations in the information sheet to explain to participants why data completion at follow-up is critical. Multiple methods of contact will be collected before the screening session (email, mobile/landline, post) to enable us to send multiple follow-up reminders. Furthermore, we will use various strategies to maintain study participants will be entered into a prize draw to win one of 50 £20 gift vouchers for completing follow-up assessments), contacting people prior to outcome assessments, sending greetings cards, and maintaining contact through study newsletters. The retention will be reviewed an ongoing basis by the Trial Management Group (TMG) and the Data Monitoring and Ethics Committee (DMEC) to flag a dropout rate of >30% and if mitigating steps need to be taken.

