- Treatment preference: Two questions asking how much they hope to receive iACT4CARERS and TAU alone without iACT4CARERS will be used (collected on a five-point Likert scale from 0 to 4).

Intervention fidelity measures

- ACT Fidelity Measure (ACT-FM [25]): All written feedback provided online by therapists will be recorded and randomly selected scripts will be reviewed and rated by independent ACT experts using an adapted form of the ACT-FM to check for intervention fidelity.
- Therapist response time: The time gap between the participant leaving a comment and their therapist providing a response will be collected for each session. Therapists are directed to provide feedback within three working days, where possible, but no later than five working days (i.e., before the next session is made available).

The scoring for each outcome measure is summarised in Table 1.

Outcome variable	Version number (if applicable)	Calculation required	Reference
GAD-7		 Sum all 7 items to calculate the total score (ranges between 0 and 21). Determine severity categories using the following cut-offs: Minimal (0-4), mild (5-9), 10-14 (moderate) and severe (15-21). The total score and severity category for each participant are automatically recorded in REDCap. However, if one or more items are missing, these fields will be left blank. 	[16]
PHQ-9		 Sum all 9 items to calculate the total score (ranges between 0 and 27). The total score for each participant is recorded in REDCap. However, if one or more items are missing, this filed will be left blank. 	[18]
CompACT		 Sum responses for each of the three subscales (Openness to Experience; Behavioural Awareness; Valued Action) and the scale as a whole (CompACT Total score). Twelve items are reverse scored before summation (items 2, 3, 4, 6, 8, 9, 11, 12, 15, 16, 18, and 19). 	[19]
		Openness to Experience (ranges between 0 and 60)	

Table 1 Outcome measure scoring

	 Calculated as the sum of scores for items: 2 (reversed), 4(reversed), 6(reversed), 8(reversed), 11(reversed), 13, 15(reversed), 18(reversed), 20, and 22. 	
	 Behavioural Awareness (ranges between 0 and 30) Calculated as the sum of scores for items: 3(reversed), 9(reversed), 12(reversed), 16(reversed), and 19(reversed). 	
	 Valued Action (ranges between 0 and 48) Calculated as the sum of scores for items: 1, 5, 7, 10, 14, 17, 21, and 23. 	
	 CompACT Total (ranges between 0 and 138) Calculated as the sum of the three subscale scores. 	

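### The protocol has no GAD-7-only fallback when a carer declines the follow-up battery, in a trial that plans for 30% loss

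*Protocol*

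**What the plan says.** The primary outcome is a single short scale at one time point. Protocol 6.5.1: "The primary outcome is anxiety symptoms as assessed by the Generalized Anxiety Disorder-7 (GAD7[30]) at 12 weeks".

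Protocol 6.6.1.2 (the section headed 12-week and 24-week Follow-Ups; two sections carry this number) sets out the online route. An email is sent at each time point. If nothing is returned within a week, the blinded Research Associate "will give a follow-up phone call to check if the participant needs additional support for completing the online assessments". If the carer "decides not to complete the assessments, the Research Associate will ask them to provide a reason if possible". No other action is given. For postal carers, the unblinded Trial Manager makes the one-week call, and no step for a refusal is described.

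Protocol 6.6.2 covers a different event, a participant who wants no more follow-up: "they no longer wish to be followed up, this view must be respected, and the participant withdrawn entirely from the trial". Data already collected are kept. Carers who stop only the treatment stay in follow-up (6.4.5 and 6.6.2).

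Protocol 6.8.2 reports that the intervention was acceptable, "although 27% of carers were lost to follow-up" in the feasibility study. It lists reminders, contact before assessments, cards, newsletters and a prize draw. On form completion, 6.6.1.1 says that "participants will be unable to submit any online questionnaire with any missing fields".

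**The concern.** Once a carer has said no to the full battery, the Research Associate is already on the phone and blinded. Seven items might still be acceptable to someone who will not answer more than sixty, but the protocol uses the moment only to ask for a reason. Table 2 allows two weeks from the scheduled date, so a call at one week leaves about one more week to obtain anything.

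What is at stake is the 12-week GAD-7. SAP 7.2 models that score. SAP 7.3.1 treats multiple imputation as a sensitivity analysis to be considered, and Protocol 6.10.4.5 ties imputation to data missing at random. Neither document specifies an analysis for data missing not at random. If refusal is related to how the carer is doing, or to arm, an observed score is worth more than any modelling of its absence. The 30% inflation in the sample size protects power; it does nothing about bias.

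**Working it through.** **1. The plan's own figure.** Inputs from Protocol 6.7 and SAP 4.3: d = 0.35, two-sided 5%, 90% power, 30% dropout. The two-sample t-test solution is 172.5, so 173 per arm. Inflating, 173 / 0.70 = 247.1, so 248 per arm and 496 in total. Both stated figures reproduce, so this is not a sample-size error.

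**2. Planned loss.** 496 × 0.30 = 148.8, about 149 carers without a primary outcome.

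**3. Size of the battery.** Item counts are from Protocol 6.5.2, with the GAD-7 from SAP Table 1; the schedule is Protocol Table 2.
- Common battery: GAD-7 (7) + PHQ-9 (9) + CompACT (23) + EACQ (15) + EQ-5D-5L (5) + ICECAP-O (5) = 64. The GAD-7 share is 7/64 = 10.9%.
- Intervention arm at 12 weeks, with the STTS-R at its stated 12 items: 76. The share is 7/76 = 9.2%.
- The modified CSRI is extra; its length is not given.

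**4. What a fallback might recover.** The documents give no recovery rate. Let f be the fraction of losses recovered, assumed to be 10%, 20% or 30%.
- Scores regained = 148.8 × f
- Remaining loss = 0.30 × (1 − f)
- Standard error ratio = √[0.70 / (0.70 + 0.30f)]

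| f | Scores regained | Remaining loss | SE ratio | Observed d (step 5) |
|---|---|---|---|---|
| 0 | 0 | 30% | 1.000 | 0.350 |
| 0.1 | 14.9 | 27% | 0.979 | 0.336 |
| 0.2 | 29.8 | 24% | 0.960 | 0.322 |
| 0.3 | 44.6 | 21% | 0.941 | 0.310 |

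The standard error falls by about 2%, 4% and 6%. Power at d = 0.35 is 90.3% with 30% loss (173.6 per arm) and 91.5% with 27% loss (181.0 per arm). The gain in power is modest.

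**5. Bias illustration.** Assume that retained intervention carers benefit by d = 0.35, lost ones not at all, that loss in the control arm is uninformative, and that recovered carers are typical of the lost.
- True ITT effect = 0.70 × 0.35 + 0.30 × 0 = 0.245
- Observed effect with no recovery = 0.35, so the bias is 0.105
- Observed effect with recovery = 0.245 / (0.70 + 0.30f), as in the last column

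At f = 0.3 the remaining bias is 0.310 − 0.245 = 0.065, and 0.065 / 0.105 = 62% of the bias is still there.

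**The case against.** The strongest reply is that the protocol already works hard before a refusal and that partial participation is allowed. The email explains why the data matter, a support call follows, and 6.8.2 adds reminders and incentives. Protocol 7.5 lets participants refuse any part of the trial. All of that stands, but none of it tells staff to ask for the GAD-7 alone.

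A reader might infer more than the text supports in two places.
- **That a carer who declines the battery is then withdrawn entirely.** The documents do not say so. Section 6.6.1.2 contains no withdrawal. Full withdrawal in 6.6.2 is triggered only when the carer wants no further follow-up. Nothing cancels the 24-week form after a declined 12-week one.
- **That a completed GAD-7 is lost if the rest of the pack is abandoned.** The rule against incomplete online submission does not say whether the battery is one form or several. SAP Table 1 records scores instrument by instrument, and at baseline the GAD-7 sits in the screening assessment, ahead of the other measures. A separately saved form may already exist.

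Three further objections also stand. An offer at refusal reaches only carers who answer the call, and the 27% feasibility loss is not split into refused and uncontactable. That disengaged carers, or the longer intervention-arm pack, drive refusal is plausible but undocumented. Reading the GAD-7 aloud turns a self-report scale into an interviewer-read one, and only among decliners.

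**Conclusion.** The gap is real but narrow. After the support call, the only written action on an online refusal is to ask for a reason, and for postal refusals there is none. No reduced-data option exists for the primary outcome, either at a single visit or for carers who stop follow-up. This is a missed opportunity in the design. It is neither a contradiction nor an error in the sample size.

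The planned loss of about 149 carers is the documents' own figure. The benefit of a fallback is not: 15 to 45 scores and a 2% to 6% smaller standard error follow only if 10% to 30% of all losses are recovered. The bias example rests on zero benefit in every lost intervention carer, and even there most of the bias remains at 30% recovery. The change is still worth making, because it is cheap and yields observed primary outcomes that no analysis can replace.

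**What to change.** **Protocol 6.6.1.2 (follow-ups).** Before a refusal is recorded, have the blinded Research Associate offer the GAD-7 alone: first as a short online link or a single posted page, and read aloud only as a last resort. Then ask for the reason. Route postal carers who decline to the same blinded Research Associate rather than leaving this with the unblinded Trial Manager.

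**Form build.** Place the GAD-7 first and save it separately, if the database does not already do so.

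**Protocol 6.6.2.** Add a recorded level of GAD-7 only from now on, short of full withdrawal. State that declining week 12 does not cancel week 24.

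**SAP 7.2.** State that GAD-7-only responses enter the primary analysis. Record the mode of completion for every score.

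**Cost.** Amendment wording, possibly a change of form order, and a few minutes per refusal. For online carers this falls on a call already being made; for postal decliners it adds a call. The downside is a small number of interviewer-read scores among decliners, which the mode flag makes identifiable. The change can help only visits still to come when it takes effect.

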6.6.2 Early Stopping of Follow-up

If a participant chooses to discontinue their trial treatment, they should continue to be followed up as closely as possible to the follow-up schedule defined in the protocol, providing they are willing. They should be encouraged and facilitated not to leave the whole trial, even though they no longer take the trial treatment. If, however, the participant exercises the view that they no longer wish to be followed up, this view must be respected, and the participant withdrawn entirely from the trial. NCTU should be informed of the withdrawal in writing using the appropriate iACT4CARERS trial documentation. Data already collected will be kept and included in analyses according to the intention-to-treat principle for all participants who stop follow-up early.

Participants who stop trial follow-up early will not be replaced.

6.6.3 Participant Transfers

UEA will obtain written consent from all participants, and UEA and NCTU will conduct all assessments remotely. Therefore, participants moving to a different area of England during the trial will not affect data collection. Participant transfers will not occur during the trial.

6.6.4 Loss to Follow-up

Multiple methods of contact will be collected before the screening session (email, mobile/landline, post) to enable us to send multiple follow-up reminders.

6.6.5 Trial Closure

The end of the trial is defined as four months following the last follow-up visit of the last participant randomised, to allow for data entry and data cleaning activities to be completed.

6.7 Sample Size

Participants in our feasibility study had an average reduction of 26% on GAD7. A reduction of 20% on GAD7 is considered to be a Minimum Clinically Important Difference[23]. Using a conservative reduction of 20% from the mean baseline GAD7 score, and using the variability estimated from our feasibility study, a clinically-meaningful effect size is estimated to be d = 0.55 for our sample. Recent systematic reviews of RCTs of self-help ACT and mindfulness-based interventions (mainly for individuals with a mental or physical health condition) demonstrated a pooled effect size of d = 0.35 for anxiety[42, 43]. One of these reviews, which solely focused on RCTs of self-help ACT[42] demonstrated that when analysis was limited to studies that utilised guided self-help ACT, the pooled effect size increased to d = 0.61, while limiting analysis to studies that used an unguided approach decreased the pooled effect size to d = 0.16. The effect size calculated from our feasibility study of iACT4CARERS, which utilised a guided approach, is in line with the effect size reported in previous reviews.

To ensure adequate statistical power, we have decided to take the most conservative approach possible and have used an effect size of d = 0.35 in our sample size calculation. To detect the effect size of d = 0.35 between the two trial arms at a two-tailed significant level of 5% with 90% statistical power, each arm requires 173 participants (i.e. 346 in total). Twenty seven percent of carers were lost to follow-up in our feasibility study. Assuming a dropout rate of 30%, a total of 496 carers will be recruited over 20 months (i.e. 24.8 participants per month).

6.8 Recruitment and Retention

6.8.1 Recruitment

In our feasibility study, 76% of participants who received iACT4CARERS had self-referred from the community, and 24% of participants were referred from NHS services[22]. Therefore, multiple recruitment strategies will be used to reach out to potential participants, and both clinician and self-referrals will be accepted.

- Recruitment through NHS PICs: PICs are most likely to be primary carer services (GPs). PICs will search their database to identify potentially eligible participants. An invitation letter, including PIS, an expression of interest card and a pre-paid return envelope, will be sent to potential participants from PICs. If interested, participants will be asked to return the expression of interest card, providing their preferred contact detail, to the study team at UEA using the return envelope. Carer-focused publicity materials (study flyer and video-recorded study advertisement) will also be made available in waiting areas of the services and on their social media platforms (e.g. twitter, Facebook, website) to promote the study.
- Recruitment through NHS trial sites: Potential participants will be identified through trial sites. These services will include Community Mental Health Teams and memory clinics. Clinicians will approach potentially eligible participants and will seek verbal consent for Research Associates based at UEA to contact the participant with further information about the study if they express interest. A nominated individual at trial sites will share contact detail of potential participants (name, telephone number and email) with UEA via the central database (REDCap), stored on

servers based at NCTU. The central database will also ask the nominated individual to indicate that they have checked the basic eligibility criteria (being a family carer, interested in online psychological support and having access to internet) and have obtained verbal consent. Research Associates will then arrange a screening appointment. Carer-focused publicity materials (study flyer and video-recorded study advertisement) will also be made available in waiting areas of the services and on their social media platforms (e.g. twitter, Facebook, website) for those who may wish to self-refer.

- Recruitment within the community: Various methods (used successfully in the feasibility study) will be used in the community to reach potential participants. This includes advertisement through local newspapers (the most successful strategy in our feasibility study) and Join Dementia Research. The study will also be advertised through relevant charities (e.g. Alzheimer's Society) and local community services (e.g. dementia cafés). Carer-focused publicity materials (study flyer and video-recorded study advertisement) will be made available through the relevant resources such as their newsletters and social media platforms (e.g. twitter, Facebook, website). These approaches will allow potential participants to self-refer to the trial via telephone, email, or the iACT4CARERS website.
- Culturally acceptable recruitment strategies: Multiple strategies recommended by our PPI members will be used to maximise the recruitment of participants from ethnic minority groups. These include advertising on TV programmes that target ethnic minority groups, such as Colors and Start Plus, visiting places of worship, contacting local faith leaders, and circulating the information through relevant social media (e.g. Facebook, twitter) and WhatsApp befriending groups which have become popular during the COVID-19 pandemic. Setting up these approaches will be supported by the collaborating partner, the Centre for Ethnic Health Research. A video-recorded study advertisement in three different languages will be produced by the Centre for Ethnic Health Research. Potential participants will be able to self-refer to the trial via telephone, email, or the iACT4CARERS website.

